3. PROTOCOL SYNOPSIS

Name of Sponsor/Company: Seattle Gummy Company	Individual Study Table Referring to Part of Dossier in Which the Individual Study or Study Table is Presented: Volume: Reference:	(For National Authority Use Only)
Name of Finished Product: Ceteric™ Allergy Gummy Regular		
Name of Active Ingredient: Cetirizine HCl		
Title: A Randomized, Open-Label, Single-Dose, Five-Period Crossover, Relative Bioavailability Study to Evaluate Cetirizine HCl Gummy 10 mg and Cetirizine HCl Oral Tablets 10 mg Administered in Healthy Adult Male and Female Subjects		
Protocol Number: P001-2019		
Investigator, Study Center: [name] Frontage Clinical Services, Inc. [name]	Bioanalytical Laboratory: Frontage Laboratories, Inc. [name]	
Phase of Development: Phase 1		
Objectives: Primary: 
 • To determine the relative bioavailability of a single oral dose of cetirizine HCl Gummy 10 mg and cetirizine HCl oral tablets 10 mg administered under fasted conditions in healthy adult male and female subjects. Secondary: 
 • To determine the relative bioavailability of a single oral dose of cetirizine HCl Gummy 10 mg administered under fasted and fed conditions in healthy adult male and female subjects; • To determine the relative bioavailability of a single oral dose of cetirizine HCl Gummy 10 mg administered under fasted conditions with and without water in healthy adult male and female subjects; • To determine the relative bioavailability of a single oral dose of cetirizine HCl Gummy 10 mg administered under fasted conditions and chewed or swallowed whole in healthy adult male and female subjects. 		
Test drug: Ceteric™ Allergy Gummy Regular 10 mg (cetirizine HCl Gummy 10 mg), manufactured by Seattle Gummy Company, [name].		
Reference drug: Zyrtec® 10 mg tablets (cetirizine HCl oral tablets 10 mg), manufactured by Pfizer labs, New York, NY 10017.		
Number of Subjects Planned: Approximately 30 eligible subjects will be randomized and dosed such that at least 24 subjects complete all five periods. The selection of sample size is empirical. However, based on the reported approximate 10% intra-subject variability of the Reference Zyrtec®10 mg tablet, it's expected that 24 completed subjects should be adequate for evaluation of relative bioavailability and PK in this single dose, 5-period crossover study. Assuming up to a 20% dropout rate, 30 subjects will be randomized in the study.		
Study Design and Methodology: This is an open-label, single dose, randomized, five-period, crossover design study to evaluate the relative bioavailability of a single oral dose of cetirizine HCl Gummy 10 mg (Test) and cetirizine HCl oral tablets 10 mg (Zyrtec®, Reference) under fasted conditions in healthy adult male and female subjects, and the impact on the bioavailability of cetirizine HCl Gummy 10 mg when administered with food, when administered with or without water, and when chewed or swallowed whole.		

Name of Sponsor/Company: Seattle Gummy Company	Individual Study Table Referring to Part of Dossier in Which the Individual Study or Study Table is Presented:	(For National Authority Use Only)
Name of Finished Product: Ceteric™ Allergy Gummy Regular		
Name of Active Ingredient: Cetirizine HCl		

Following a screening period of up to 28 days, eligible subjects will be enrolled and randomized to receive study drug. Subjects will be confined to the Clinical Research Unit (CRU) for two overnight stays during each of the five study periods.

Eligible subjects will receive a single oral dose of one of five treatments (Treatments A, B, C, D or E) in five separate periods in a randomly assigned sequence, with each treatment separated by an approximate 5-day washout period. In each study period dosing will occur in the morning after an overnight fast of at least 10 hours.

All doses will be administered under fasted conditions except for Treatment C, when cetirizine HCl Gummy 10 mg will be administered after consumption of a high-calorie, high-fat breakfast.

All doses will be administered with approximately 240 mL of room temperature water except for Treatment D, when cetirizine HCl Gummy 10 mg dose will be administered without water.

All doses of cetirizine HCl Gummy 10 mg will be chewed before swallowing except for Treatment E, when subjects will be instructed to swallow the dose whole.

Treatment	Treatment Description
A	Test: Single oral dose of cetirizine HCl Gummy 10 mg, chewed, administered with approximately 240 mL of room temperature water, under fasted conditions
B	Reference: Single oral dose of cetirizine HCl oral tablets 10 mg, administered with approximately 240 mL of room temperature water, under fasted conditions
C	Test: Single oral dose of cetirizine HCl Gummy 10 mg, chewed, administered with approximately 240 mL of room temperature water, under fed conditions
D	Test: Single oral dose of cetirizine HCl Gummy 10 mg, chewed, administered with no water, under fasted conditions
E	Test: Single oral dose of cetirizine HCl Gummy 10 mg, swallowed whole, administered with approximately 240 mL of room temperature water, under fasted conditions

In each study period, confinement to the CRU will begin the day prior to dosing during each period and continue until after collection of the 36-h pharmacokinetic (PK) post-dose sample the evening of the day following dosing. Subjects will be discharged from the study after exit procedures are completed on Day 22 in Period 5, or after Early Termination.

Following an overnight fast of at least 10 hours, subjects will receive a single oral dose of their assigned study drug with approximately 240 mL of room temperature water (except when assigned to Treatment D) at approximately 0800 hours (± 1 hour). Subjects assigned to Treatment C will consume a standardized high calorie, high fat breakfast within approximately 30 minutes prior to dosing.

During each of the five study periods, serial PK blood samples to measure plasma concentrations of cetirizine will be collected by direct venipuncture or by use of an indwelling cannula prior to dosing (up to 60 minutes prior to dosing), 10, 20 minutes post-dose and 0.5, 1, 1.5, 2, 2.5, 3, 4, 6, 8, 10, 12, 24, 36 hours post-dose. Where PK sampling time points coincide with vital sign measurements, vital signs will be collected ± 10 minutes of the scheduled time point, and PK samples will be collected at the scheduled time point.

Height and weight will be measured and body mass index (BMI) will be calculated at Screening. A full physical examination (PE) will be performed at Screening, and an abbreviated PE will be performed at the Study Exit/Early Termination Visit. Physical examinations may be repeated prior to study discharge as deemed necessary by the Investigator or in response to adverse events (AEs).

Demographic information, medical history, and concomitant medication use (prescribed and over-the-counter [OTC] medications, including vitamin/supplement use) will be obtained at the Screening

Name of Sponsor/Company: Seattle Gummy Company	Individual Study Table Referring to Part of Dossier in Which the Individual Study or Study Table is Presented:	(For National Authority Use Only)
Name of Finished Product: Ceteric™ Allergy Gummy Regular		
Name of Active Ingredient: Cetirizine HCl		

Visit. A review of all medications will be repeated at each Check-in and at Study Exit/Early Termination. Subjects will be queried from Check-in for Period 1 through Study Exit/Early Termination as to any changes in their overall health, and all treatment-emergent adverse events (TEAE) will be captured and documented throughout the study from the time a subject receives the first dose of study drug until 7 days after the subject receives the last dose of study drug.
 
A resting (i.e. after at least 5 minutes rest in the supine position) 12-lead electrocardiogram (ECG) will be obtained at the Screening Visit. Electrocardiograms may be repeated at other times as deemed necessary by the Investigator or in response to AEs. Seated (i.e., after at least 3 minutes rest in the sitting position) vital signs, including systolic blood pressure (SBP), diastolic blood pressure (DBP), pulse rate (PR), respiration rate (RR) and oral temperature, will be measured at the Screening Visit, and seated SBP, DBP and pulse rate will be measured within 120 minutes prior to each dose and at approximately 1, 4, 8 and 10 hours post-dose in each study period and at Study Exit/Early Termination.
 
Clinical laboratory testing (chemistry, hematology, urinalysis) will be conducted at the Screening Visit and at Study Exit/Early Termination.
 
Serology testing (HIV 1/2 antibodies, Hepatitis B surface antigen, Hepatitis C antibody) will be performed at Screening only. All subjects will undergo urine drug and saliva alcohol testing at Screening and at each Check-in Visit. Female subjects will have a serum pregnancy test at Screening and a urine pregnancy test at each Check-in Visit. Postmenopausal females will have serum follicle-stimulating hormone (FSH) and estradiol levels measured at Screening to confirm postmenopausal status.
 
A total of approximately 420 mL (6 mL x 14 x 5 periods) of blood will be collected over the five study periods for determination of plasma cetirizine. Additionally, blood samples (approximately 35 mL) will be obtained at Screening and Discharge/Early Termination for chemistry, hematology and serology evaluations, for a total of approximately 455 mL of blood collected during the study.
		
Duration of Treatment: Total length of study participation will be approximately 23 days (excluding up to 28 days of screening).		
Selection of Subjects: Inclusion Criteria: 
 1. Are capable of giving informed consent and complying with study procedures; 2. Male or female, 18 to 55 years of age, inclusive, at date of consent; 3. Body mass index (BMI) ≥ 18.0 to ≤ 32.0 kg/m² and total body weight > 50 kg (110 lbs.) at Screening; 4. All female subjects must have a negative pregnancy test at Screening and at each Check-in Visit; and one of the following: 
 a. Using a medically acceptable form of birth control for at least 1 month prior to first dose [e.g., hormonal contraceptives (oral, patch, injectable or vaginal ring), intrauterine device, or a double barrier method (e.g., diaphragm, cervical cap, oral, patch or vaginal hormonal contraceptive, condom, spermicide, or sponge)] b. Documented as surgically sterile by hysterectomy, bilateral oophorectomy, bilateral salpingectomy, or bilateral tubal ligation/tubal occlusion) at least 6 months prior to the first dose; c. Postmenopausal (no menstruation for a minimum of 12 months and confirmed by FSH and estradiol at Screening); 5. Medically healthy based on medical history, vital sign measurements, clinical laboratory test results, and physical examination; 6. Non-smokers (including nicotine-containing products) for at least 6 continuous months prior to the first dose. 7. Be willing and able to consume all contents of the standardized high calorie, high fat breakfast within 30 minutes prior to dosing. Exclusion Criteria:		

Name of Sponsor/Company: Seattle Gummy Company	Individual Study Table Referring to Part of Dossier in Which the Individual Study or Study Table is Presented: Volume: Reference:	(For National Authority Use Only)
Name of Finished Product: Ceteric™ Allergy Gummy Regular		
Name of Active Ingredient: Cetirizine HCl		

 1. Females who are pregnant, lactating, or planning to become pregnant during the study; 2. Life-time history and/or recent evidence of alcohol or drug/substance abuse disorder; 3. Subjects with history of hypersensitivity to cetirizine or hydroxyzine, or any component of the test and reference formulations; 4. Subjects who test positive at Screening for human immunodeficiency virus (HIV), Hepatitis B surface antigen (HBsAg), or Hepatitis C virus (HCV) antibody; 5. Subjects who test positive at Screening or at Check-in for alcohol and/or drugs of abuse; 6. Subjects who donated ≥ 500 mL of blood within 56 days prior to the first dose of study drug or ≥ 50 mL and ≤ 499 mL of blood within 30 days or plasma (e.g. plasmapheresis) within 14 days prior to the first dose of study drug; 7. Use of prescription or non-prescription drugs, dietary supplements, or herbal supplements at the time of Screening and within 14 days prior to the first dose of the study drug; 8. Subjects who have a history of difficulty in donating blood or difficulty with phlebotomy procedures, and poor venous access; 9. Subjects who have participated in another clinical trial within 30 days prior to the first study period; 10. Member or first-degree relative of study staff or the Sponsor directly involved in the study; 11. Any condition which in the opinion of Investigator would interfere with the subject's ability to provide informed consent, comply with study instructions, confound interpretation of study results, or endanger the subject if he or she took part in the trial. 		

Pharmacokinetic and Safety Variables
 
Pharmacokinetic: Plasma concentrations of cetirizine will be measured and PK parameters, including C_{max}, T_{max}, AUC_{0-t}, $AUC_{0-\infty}$, K_{el} and $t_{1/2}$, will be determined using non-compartmental analysis methods (Phoenix WinNonlin software, version 8.1 or higher, Certara USA Inc., Princeton, NJ).
 
Safety: Safety will be based on the frequency of AEs and changes in vital signs, clinical laboratory assessments and PE findings.
 
Statistical Methods and Planned Analysis: The primary PK endpoints will be maximum plasma cetirizine concentration (C_{max}), and area under the plasma drug concentration versus time curve calculated to the last measurable observation (AUC_{0-t}) and extrapolated to infinity ($AUC_{0-\infty}$).
 
The secondary PK endpoints will be time to C_{max} (T_{max}), elimination half-life ($t_{1/2}$) and terminal elimination rate constant (K_{el}).
 
The safety and tolerability of single 10 mg oral doses of cetirizine HCl, as assessed by incidence of TEAEs, study discontinuation information, laboratory test results, vital signs and PE findings will be secondary endpoints.
 
Relative Bioavailability Comparisons: The following comparisons will be assessed:
 
Treatment A / Treatment B The relative bioavailability of the Test formulation (cetirizine HCl Gummy 10 mg, chewed) administered with 240 mL room temperature water under fasted conditions will be compared to the Reference formulation (cetirizine HCl oral tablets 10 mg) administered with 240 mL room temperature water under fasted conditions;
 
Treatment A / Treatment C The relative bioavailability of the Test formulation (cetirizine HCl Gummy 10 mg, chewed) administered with 240 mL room temperature water under fasted conditions will be compared to the Test formulation
		

Name of Sponsor/Company: Seattle Gummy Company	Individual Study Table Referring to Part of Dossier in Which the Individual Study or Study Table is Presented: Volume: Reference:	(For National Authority Use Only)
Name of Finished Product: Ceteric™ Allergy Gummy Regular		
Name of Active Ingredient: Cetirizine HCl		

(cetirizine HCl Gummy 10 mg, chewed) administered with 240 mL room temperature water under fed conditions;
 
Treatment A / Treatment D
 
The relative bioavailability of the Test formulation (cetirizine HCl Gummy 10 mg, chewed) administered with 240 mL room temperature water under fasted conditions will be compared to the Test formulation (cetirizine HCl Gummy 10 mg, chewed) administered without 240 mL room temperature water under fasted conditions;
 
Treatment A / Treatment E
 
The relative bioavailability of the Test formulation (cetirizine HCl Gummy 10 mg, chewed) administered with 240 mL room temperature water under fasted conditions will be compared to the Test formulation (cetirizine HCl Gummy 10 mg, swallowed whole) administered with 240 mL room temperature water under fasted conditions.
 
For each of the comparisons, confidence intervals (CIs; 90%) will be constructed to test the two one-sided hypotheses at the $\alpha = 0.05$ level of significance for C_{max}, AUC_{0-t} and $AUC_{0-\infty}$. Log-transformed PK parameters C_{max}, AUC_{0-t} and $AUC_{0-\infty}$ will be analyzed using an analysis of variance (ANOVA) model with fixed effects for treatment and sequence, and a random effect of subject nested in sequence.
 
The arithmetic means, geometric means, and ratio of the geometric means and 90% CIs on the ratios of each comparison will be displayed.
 
Nonparametric analyses of T_{max} and $t_{1/2}$ (between Test and Reference formulations) may be performed using Wilcoxon Signed Rank Test. The corresponding 95% CI for the difference in medians will be reported using Walsh Averages and 25th and 75th percentiles of the Wilcoxon Signed Rank Statistic Test.
 
Plots of mean concentrations of plasma cetirizine versus time will be generated for each treatment group. Individual concentrations versus time graphs will also be provided.
 
Statistical tables will be generated using SAS version 9.4 or higher.
 
Adverse events will be coded using a standardized Medical Dictionary for Regulatory Activities (MedDRA), Version 22,0 or higher. Prior and concomitant medications will be coded using the World Health Organization (WHO) Drug Enhanced Dictionary (March 2019 or later). The proportion of subjects experiencing AEs will be summarized by treatment group. Tabulations will be prepared including all AEs and all AEs by relationship and severity. Adverse events resulting in early termination and events meeting regulatory criteria for seriousness will also be tabulated separately. By-subject listings of all safety data and concomitant medication use will be generated.

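### The blood-volume figure counts 14 PK samples per period, but the sampling schedule lists 16; at 6 mL per sample the total is about 515 mL, not 455 mL

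*Protocol*

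**What the plan says.** Everything relevant is in the Protocol, section 3 (Protocol Synopsis), under Study Design and Methodology, plus the Duration of Treatment entry.

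- **Sampling schedule.** It applies to every period: "During each of the five study periods, serial PK blood samples to measure plasma concentrations of cetirizine will be collected". The draws begin with a pre-dose sample, "prior to dosing (up to 60 minutes prior to dosing), 10, 20 minutes post-dose", and the post-dose times in full are "10, 20 minutes post-dose and 0.5, 1, 1.5, 2, 2.5, 3, 4, 6, 8, 10, 12, 24, 36 hours post-dose".
- **PK blood volume.** "A total of approximately 420 mL (6 mL x 14 x 5 periods) of blood will be collected over the five study periods".
- **Laboratory blood.** "Additionally, blood samples (approximately 35 mL) will be obtained at Screening and Discharge/Early Termination", covering chemistry, hematology and serology.
- **Total.** "for a total of approximately 455 mL of blood collected during the study".
- **Time span.** "Total length of study participation will be approximately 23 days (excluding up to 28 days of screening").

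**The concern.** The volume paragraph prints its own calculation, and the multiplier for samples per period is 14. The schedule a few paragraphs earlier lists 16 times. Both describe the same draws in the same five periods.

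What is at stake is the accuracy of a burden statement. The subjects are healthy volunteers, and this is the only place in the protocol text that says how much blood is taken from each of them. If the site follows the schedule and draws 6 mL each time, the protocol understates that amount. The mismatch also gives two planned sample counts per subject. The sample size, the PK endpoints and the bioavailability comparisons do not use the figure.

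**Working it through.** **Inputs**, all from Protocol section 3:

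- volume per PK sample: 6 mL
- samples per period in the volume calculation: 14
- periods: 5
- laboratory blood: about 35 mL
- listed sampling times: as in the schedule quoted above

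**Step 1. Reproduce the stated figures.** PK volume = mL per sample × samples per period × periods = 6 × 14 × 5 = 420 mL. Total = 420 + 35 = 455 mL. Both agree with the protocol, so the multiplication is sound and only the count of 14 is in question.

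**Step 2. Count the schedule.**

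- pre-dose: 1
- in minutes (10, 20): 2
- in hours (0.5, 1, 1.5, 2, 2.5, 3, 4, 6, 8, 10, 12, 24, 36): 13
- sum: 1 + 2 + 13 = 16 per period

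**Step 3. Recompute with 16.**

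| Quantity | Volume paragraph (14) | Listed schedule (16) | Difference |
|---|---|---|---|
| PK blood per period | 6 × 14 = 84 mL | 6 × 16 = 96 mL | 12 mL |
| PK blood, five periods | 420 mL | 96 × 5 = 480 mL | 60 mL (60/420 = 14.3%) |
| Total with 35 mL | 455 mL | 480 + 35 = 515 mL | 60 mL (60/455 = 13.2%) |
| PK samples per subject | 14 × 5 = 70 | 16 × 5 = 80 | 10 |

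**Step 4. Look for a reading that gives 14.**

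- Post-dose samples only: 16 − 1 = 15, giving 6 × 15 × 5 = 450 mL. This does not match.
- Dropping any two listed times, for instance those at 10 and 20 minutes, gives 14 and 420 mL. Nothing in the protocol says that a listed sample is not drawn.
- Keeping 420 mL with 16 samples needs 420 / (16 × 5) = 5.25 mL per draw, which contradicts the stated 6 mL.

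**Step 5. Time frame.** The 515 mL includes the screening blood, so it extends over at most about 28 + 23 = 51 days. The protocol does not split the 35 mL between Screening and exit. On the listed schedule, the draw after Screening is therefore at least 480 mL and less than 515 mL, because some of the 35 mL is taken at Screening.

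**The case against.** The strongest case on the other side concerns weight, not the count.

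- **The figure drives nothing.** No analysis uses it, and the protocol sets no cap on study blood. The volume thresholds in exclusion criterion 6 concern donation before the first dose. This is correct, and the point should not be presented as a breach of a limit or a threat to validity.
- **The schedule is the operative instruction.** It names each time, while the volume paragraph only carries a multiplier. A site would draw 16 samples, so the sample count is hardly in doubt in practice, and the multiplier is the likelier slip. That is plausible, but the text does not prove it. If the schedule does govern, the stated volume is the element that is too low, which is the concern itself.
- **The volume is given as approximate.** That wording could cover rounding or variation in the draw. It does not cover an explicit count of 14 where 16 are listed.
- **Consent pages are not at hand.** Nothing can therefore be concluded about what subjects were told. This is also correct, and it limits the point to the protocol text.
- **The totals assume completion.** The 420 and 480 mL figures both suppose that a subject finishes all five periods, while the protocol allows for up to 20% dropout. This lowers the volume for those who leave early but affects both counts, so it does not remove the discrepancy.

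**Conclusion.** The concern holds. At 6 mL per sample, the listed schedule implies 480 mL of PK blood and about 515 mL in total for a subject who completes all periods, against the stated 420 and 455 mL. The protocol's figure is 60 mL too low if the schedule and the 6 mL are both as intended. The protocol does not show which of the three elements (schedule, volume per sample, total) is wrong, only that they conflict.

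The result rests on two assumptions: that each listed time is one 6 mL draw, and that the PK draws and the 35 mL of laboratory blood are separate, as the protocol's own addition treats them. The error should be corrected because it misstates volunteer burden. It does not affect the statistical conclusions.

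**What to change.** Reconcile the sampling schedule with the blood-volume paragraph in section 3.

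- If the 16 listed times and 6 mL per sample stand, change the multiplier from 14 to 16, the PK volume from 420 to 480 mL and the total from 455 to about 515 mL.
- If 14 samples were intended, the schedule must show which two listed times are not drawn.
- If 420 mL was intended with 16 samples, the volume per sample must be restated, since 420 mL over 80 samples is 5.25 mL each.

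Whichever applies, check that any other study document quoting the blood volume carries the same figure. The cost is three numbers in one paragraph, or one edit to the schedule or the volume per sample. The only drawback is that the stated blood volume may rise.

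### Does Exclusion 7's bar on drug use shut out the women on hormonal contraception whom Inclusion 4a accepts?

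*Protocol*

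**What the plan says.** Both rules are in section 3 of the Protocol, under Selection of Subjects.

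- **Inclusion 4a** is one of three routes by which a woman can qualify. It accepts a medically acceptable "form of birth control for at least 1 month prior to first dose [e.g., hormonal contraceptives (oral, patch, injectable or vaginal ring"), and then names an intrauterine device or a double barrier method. Hormonal methods appear again among the double-barrier examples: "diaphragm, cervical cap, oral, patch or vaginal hormonal contraceptive, condom, spermicide, or sponge".
- **Exclusion 7** excludes "Use of prescription or non-prescription drugs, dietary supplements, or herbal supplements at the time of Screening and within 14 days prior" to the first dose. It has no exception.
- **Timing**, from Study Design and Methodology: "Following a screening period of up to 28 days, eligible subjects will be enrolled and randomized to receive study drug".
- **Other medication text** provides for collecting, coding and listing medications and for repeat checks: "A review of all medications will be repeated at each Check-in and at Study Exit/Early Termination". None of it exempts contraceptives.
- **Exclusion 11** lets the investigator exclude for any condition that would, among other things, "confound interpretation of study results, or endanger the subject if he or she took part in the trial". It adds grounds to exclude and cannot waive another criterion.

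**The concern.** Inclusion and exclusion criteria apply together, so meeting 4a does not override an exclusion. A contraceptive pill, patch or ring is a drug in ordinary language, and a woman who has used one without a break for a month is using it at Screening and in the two weeks before dosing. The same protocol therefore appears to invite her in and shut her out.

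If that were left to chance, a site could screen-fail women whom 4a calls eligible, or enrol them and record each as an eligibility deviation, and two members of staff could decide the same case differently. The table of contents lists only general information, contents and the synopsis, so it points to no later section that could supply the missing exception. Eligibility is also not something normally left to a statistical analysis plan.

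**Working it through.** The protocol gives no figure for this point, so the check sets the passages side by side and then asks whether anything statistical depends on the answer.

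**1. Do the time windows overlap?** Inputs: use for at least 1 month (4a), a 14-day window (Exclusion 7), and screening of up to 28 days.

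- The 14-day limb is always met by an uninterrupted user, because 1 month is longer than 14 days.
- The Screening limb is met whenever use began on or before the Screening visit. If the 28 days run up to first dose, a month of 28 to 31 days always covers it.
- If the Check-in day falls outside the 28 days, Screening could be 28 + 1 = 29 days before dosing. The schedule suggests this. With doses about 5 days apart and first dose on Day 1 (an inference), the fifth dose is on Day 1 + 4 × 5 = 21 and exit is on Day 22. Adding the Check-in day gives the stated 23 days of participation, which excludes screening. A month taken as 28 days then falls one day short of the earliest possible Screening, while 30 or 31 days still covers it.

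Apart from that one-day edge, the overlap follows directly from uninterrupted use. Counting Screening days would only restate that assumption.

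**2. Which methods are caught?**

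| Method named in 4a | Caught by Exclusion 7 as written? |
|---|---|
| Oral, patch, vaginal ring, uninterrupted | Yes |
| Injectable last given more than 14 days before dosing | Not settled: the text does not say whether this is use within the window |
| Spermicide | Not settled: the text does not say whether it is a non-prescription drug |

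The conflict is clear for the first row and open for the other two.

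**3. Does any stated figure move?** The sample size step is 30 × (1 − 0.20) = 24 completers. The 20% is dropout after randomization, whereas a woman refused under Exclusion 7 is lost before it and another candidate can be screened. The target of 24 is defined by completing all five periods, not by being free of eligibility deviations.

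**4. Do the comparisons move?** Write the log of C_max or AUC for subject *i* under treatment *k* as

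log Y(i,k) = μ + τ(k) + s(i) + e(i,k),

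leaving out the sequence term, which like s(i) is constant within a subject. For A versus B the within-subject difference is

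log Y(i,A) − log Y(i,B) = τ(A) − τ(B) + e(i,A) − e(i,B).

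The subject term s(i), which carries any constant effect of a background contraceptive, has dropped out. The same holds for A versus C, D and E. If a cyclic method made the background vary across the five periods, the random sequence would spread that variation over treatments as extra residual noise, not as a systematic shift. The cancellation would fail only if a contraceptive changed absorption differently between treatments, and nothing in the protocol suggests that.

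**The case for a change.** The strongest case for acting is that the contradiction is textual and not a matter of taste. Two operative criteria disagree, no exception is written anywhere, hormonal methods are the first that 4a lists, and one edited line would settle the matter without adding any procedure. Reading 4a as the exception is an inference. All of this stands.

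What it does not supply is a consequence for the trial's conclusions. No figure changes, no bias in the ratios follows, and no gain in power, precision or safety is identified. The argument that staff will decide differently has less force with one study center than it would across many. Inclusion 4a is also the specific rule and names these methods twice, so its drafters can hardly have meant Exclusion 7 to remove them without saying so.

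A related point is that Exclusion 7 joins its two time points with *and*, whereas Exclusion 5 uses *or*: "Subjects who test positive at Screening or at Check-in for alcohol and/or drugs of abuse". Taken strictly, the *and* would let through someone who was drug-free at Screening and took a drug in the last 14 days. That reading is strained. Exclusion 8 also uses *and* loosely, the natural sense of Exclusion 7 is a list of two prohibited times, and medication use is reviewed again at Check-in.

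**Conclusion.** The two criteria do conflict as written for women on uninterrupted oral, patch or ring contraception, and the text leaves injectables and spermicide unsettled. This is a missing exception that study staff can fill sensibly, and it does not weaken the design or the analysis. Its reach is screen failures and deviation counts. Its size cannot be stated, because the protocol does not give the share of candidates using such methods.

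The 30-to-24 sample size step and the four within-subject comparisons hold whether Exclusion 7 is applied literally or 4a is treated as the exception. This rests on two assumptions: that a contraceptive acts alike under all five treatments, and that an eligibility deviation of this kind does not by itself remove a completer from the pharmacokinetic analysis. The protocol states no rule to the contrary on either. If the criteria are reopened for another reason, a line reconciling 4a with Exclusion 7 would be good housekeeping, and which way to word it is for the sponsor. The plan does not need a change on this account.
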